The FLU-PRO and Flu-iiQ™ domain scores will be presented descriptively over time using descriptive statistics. A linear mixed model will be used to analyze composite symptom scores over time, per domain. For the Flu-iiQ™ a daily score will be derived averaging observed scores before the analysis. Baseline subject characteristics will be included (in particular baseline score) in case these provide to be predictive of post-baseline scores. Mean differences between treatment arms will be derived from this model using appropriate contrasts and will be presented including the associated 95% CI. For both measures, an AUC of composite symptom scores over a 7- and 14-day period per domain will be calculated and compared using a mixed model for repeated measurements.

Other PRO endpoints that will be analyzed are:

1. Time to return to usual activity and usual health (Questions 5 and 9 of the additional items for the Flu-PRO).
2. Time to significant reduction in influenza symptom severity.
3. Proportion of patients with a significant reduction (to mild or none for all influenza symptoms) at each assessment.

Other Outcomes

The length of overall hospital stay will be calculated from the date of first study drug intake up to the date of discharge. Subjects still hospitalized at the end of the study will be censored at the last contact. Data will be presented using Kaplan-Meier curves. For a comparison between treatment arms, the time to hospital discharge in days will be analyzed using an accelerated failure time model (if the data provide an acceptable model fit) or alternatively a Cox proportional hazards model (in case the hazards are proportional). Additionally, the time to event data will be analyzed using the Gehan-Wilcoxon method. The time to resumption of normal daily activities will be analyzed in an analogous fashion.

Resistance Analyses

The results of viral sequencing and phenotyping will be evaluated by the sponsor virologist. Additional exploratory characterization of the viral genotype and phenotype may be performed and will be reported accordingly.

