1.4. Sample Size Justification

Up to 90 subjects in total will be enrolled in this study. An effort will be made to include at least 24 subjects for each cohort, with the total of subjects allowed to be recruited across both cohorts. It is anticipated that it is feasible to recruit at least 60 subjects, which would lead to an acceptable precision for the primary objective.

For the primary objective of evaluating the PK of JNJ-63623872 across age cohorts the PK parameters considered of major importance are C_{min} , C_{max} , and AUC_{12h} . As there are no data available where Day 3 has been part of extensive PK sampling on the 600 mg bid dose, the variability on days with available data are presented in Table 1. Based on those data a between-subjects CV of 60% was assumed as a reasonably conservative estimate for the current study.

Table 1: Variability for Key Pharmacokinetic Parameters for JNJ-63623872 600 mg bid (Between-subjects %CV)

Time point	N	C_{min}	C_{max}	AUC_{12h}
Day 1	12	NA	65	56
Day 5	18	77	57	61
Day 5*	18	48	57	46
Day 10	12	56	44	43

Note: Based on study 63623872FLZ1001.

*JNJ-63623872 600 mg bid + oseltamivir 75 mg bid.

NA: Not applicable.

For age cohorts it was assumed that the number of hospitalizations would be about equal for elderly and non-elderly adults. In case 60 subjects are enrolled, there are 40 subjects on active treatment and it is assumed that at least 16 subjects are on active treatment in each cohort). For the comparison of PK parameters of the cohort of elderly adults (test) vs. non-elderly adults (reference) with PK data in a 16 to 24 ratio and a between-subject coefficient of variation (CV) of 60%, the 90% confidence interval (CI) of the geometric mean ratio (GMR) for C_{min} would be predicted to have a half-width of 35%, indicating that we can be 90% confident that the true GMR is in the interval observed GMR/1.35 to 1.35*GMR. If 90 subjects were enrolled with 60 on active treatment in a 24 to 36 ratio, the predicted half-width would be 28%.

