1.5. Randomization and Blinding

Central randomization will be implemented in this study. Subjects will be randomly assigned to 1 of 2 treatment arms in a 2:1 ratio (active vs. placebo) based on a computer-generated randomization schedule prepared before the study by or under the supervision of the sponsor. The randomization will be balanced by using randomly permuted blocks and will be stratified by age cohort. An interactive web response system (IWRS) will assign a unique treatment code, which will dictate the treatment assignment and matching study drug kit for the subject. The requestor must use his or her own user identification and personal identification number when contacting the IWRS, and will then give the relevant subject details to uniquely identify the subject.

The investigator will not be provided with randomization codes. The codes will be maintained within the IWRS, which has the functionality to allow the investigator to break the blind for an individual subject.

Data that may potentially unblind the treatment assignment (ie, study drug plasma concentrations) will be handled with special care to ensure that the integrity of the blind is maintained and the potential for bias is minimized. This can include making special provisions, such as segregating the data in question from view by the investigators, clinical team, or others as appropriate until the time of database lock and unblinding.

Under normal circumstances, the blind should not be broken until all subjects have completed the study and the database is finalized. Otherwise, the blind should be broken only if specific emergency treatment/course of action would be dictated by knowing the treatment status of the subject. In such cases, the investigator may in an emergency determine the identity of the treatment by contacting the IWRS. It is recommended that the investigator contact the sponsor or its designee if possible to discuss the particular situation, before breaking the blind. Telephone contact with the sponsor or its designee will be available 24 hours per day, 7 days per week. In the event the blind is broken, the sponsor must be informed as soon as possible. The date, time, and reason for the unblinding must be documented by the IWRS, in the appropriate section of the electronic case report form (eCRF), and in the source documents. The documentation received from the IWRS indicating the code break must be retained with the subject's source documents in a secure manner.

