For this endpoint the difference of active dosing regimen versus placebo will be estimated using the accelerated failure time model. The model will use the parametric shape, selected based on the goodness of fit criterion (AIC), and may take a Weibull, log-logistic, lognormal, or gamma distribution. As baseline covariates the baseline composite score and age category (≥ 18 - < 65 years, ≥ 65 - ≤ 85 years) will be included. From this model the ratio of adjusted geometric means and the 95% confidence interval will be derived comparing the active treatment versus placebo.

The Kaplan-Meier estimates will be tabulated and a figure with the Kaplan-Meier curves of the time to resolution of influenza symptoms will be added by treatment group, overall and by age group.

One stratified Cox proportional hazard model will be used to derive the Hazard Ratio for the active treatment in comparison to placebo. A Log (-Log) plot of survival will be added to check the proportional hazard assumption. Additionally, the time to event data will be analyzed using the logrank test and the Gehan-Wilcoxon method.

All analyses of Time to Resolution of Influenza will also be repeated using all 10 influenza symptoms included in Module 1 of the Flu-iiQTM instrument.

Kaplan-Meier curves will also be provided for each individual influenza symptom separately.

▪ **Time to Definitive Resolution of Influenza**

Time to definitive resolution is defined as the first of a successive series of 2 recordings in which all symptom scores for each of the 2 assessments are 0 or 1 for all 7 primary influenza symptoms of the Flu-iiQTM (cough, sore throat, headache, nasal congestion, feeling feverish, body aches or pains, and fatigue (tiredness)) AND after which all following assessments also indicate resolution (all symptom scores 0 or 1 for all 7 primary influenza symptoms) or are missing.

Definitions for a successive series of 2 recordings over time are the same as for the Time to Resolution of Influenza. Also censoring will be done similarly as for the Time to Resolution of Influenza.

The Time to Definitive Resolution of Influenza will be analyzed similarly as the Time to Resolution of Influenza.

▪ **Composite symptom score AUC:**

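### The Cox model behind the only hazard ratio for time to symptom resolution names neither strata nor covariates, although the AFT model for the same endpoint adjusts for baseline symptom score and age

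*SAP*

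**What the plan says.** SAP 4.2.3, under Time to Resolution of Influenza, specifies two regression models for one endpoint.

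- **AFT model.** This is the named estimator: "For this endpoint the difference of active dosing regimen versus placebo will be estimated using the accelerated failure time model". Its adjustment is explicit: "As baseline covariates the baseline composite score and age category". Its output is a time ratio: "From this model the ratio of adjusted geometric means and the 95% confidence interval will be derived comparing the active treatment versus placebo".
- **Cox model.** In a separate paragraph, after the Kaplan-Meier outputs: "One stratified Cox proportional hazard model will be used to derive the Hazard Ratio for the active treatment in comparison to placebo". The only further detail is a log(-log) plot to check proportional hazards. Logrank and Gehan-Wilcoxon analyses follow, also without covariates.

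The stratification factor is not named. Age is the natural inference, because SAP 1.5 says: "The randomization will be balanced by using randomly permuted blocks and will be stratified by age cohort". SAP 3.3 repeats the two age strata.

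All analyses are repeated for the 10-symptom version, and time to definitive resolution is to be analysed in a similar way. At least three hazard ratios therefore rest on the Cox sentence, and four if definitive resolution is also run on 10 symptoms.

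**The concern.** For the other time-to-event endpoints (SAP 4.2.1, 4.2.2, 4.2.4, 4.2.6 and 4.2.9), Cox is a fallback if the AFT model fits poorly. It follows directly on the AFT covariate list, so one can fairly read it as inheriting those covariates. In 4.2.3 the Cox model is unconditional and its stratification sets it apart from the AFT model, and nothing says that it takes over the AFT covariates. A programmer following the text would fit treatment and strata only.

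The term at issue is likely to matter. The baseline composite score is the mean of the seven primary symptoms on a 0-3 scale, and the event is those same seven symptoms all reaching 0 or 1. Section 4.2.3 also has no counterpart to the vital-signs rule in 4.2.1 that censors at entry subjects who already meet the criterion. A subject who starts with low scores has little or no distance to travel.

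Three things are at stake:

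- The hazard ratio would be marginal with respect to baseline severity while the companion time ratio is conditional on it. The two could disagree for that reason alone.
- With 20 to 30 controls, chance imbalance in baseline severity enters the hazard ratio unadjusted.
- Two programmers could produce different hazard ratios from the same sentence, and the choice could fall after unblinding.

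**Working it through.** **The plan's own figures.** The documents give no hazard ratio, event number or power for this endpoint, so there is nothing of that kind to reproduce. The sample size rests on PK precision. With half-width = exp(t(0.95, n1+n2-2) × √ln(1+CV²) × √(1/n1+1/n2)) - 1 and CV 60%, 16 vs 24 subjects give 35.2% and 24 vs 36 give 27.7%, against 35% and 28% stated in SAP 1.4. These agree but do not bear on this endpoint.

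**Inputs from the documents.** Allocation (SAP 1.5): "Subjects will be randomly assigned to 1 of 2 treatment arms in a 2:1 ratio (active vs. placebo"). Maximum size (SAP 1.4): "Up to 90 subjects in total will be enrolled in this study", hence 90 × 2/3 = 60 active and 30 placebo. The anticipated minimum of 60 gives 40 and 20. There are two age strata and follow-up to Day 28.

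**Assumptions not in the documents.**

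- Conditional hazard ratio 1.0, 1.5 or 2.0.
- Standardised baseline score with effect γ from 0 to 1.0 log-HR per SD, a higher score slowing resolution.
- Weibull times, shape 1.3, reference median 6 days; age effect 0.3 log-HR.
- Censoring at 28 days plus light random drop-out; 81% to 91% of subjects have events.
- Two-sided 5% threshold, used only as a yardstick.

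**Model.** Within age stratum s, hazard = h0s(t) × exp(β × treatment - γ × score). Each simulated trial was analysed by age-stratified Cox regression with and without the score, with 6,000 trials per setting.

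**Cross-check.** Schoenfeld power = Φ(√(d × 2/3 × 1/3) × ln HR - 1.96). For d = 80 and HR 2.0: √17.78 × 0.693 - 1.96 = 0.96, giving 83%. For HR 1.5 it gives 40%. The simulation with a non-prognostic score gives 78% and 35%, the same order.

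**Results, N = 90, conditional HR 2.0**

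| γ per SD | Median HR without score | Median HR with score | Rejection without | Rejection with |
|---|---|---|---|---|
| 0 | 2.00 | 2.02 | 78.2% | 78.2% |
| 0.25 | 1.93 | 2.02 | 74.9% | 77.9% |
| 0.5 | 1.81 | 2.01 | 65.5% | 77.6% |
| 0.75 | 1.68 | 2.00 | 53.5% | 75.8% |
| 1.0 | 1.60 | 2.02 | 45.2% | 76.4% |

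- **N = 90, HR 1.5.** Without the score, the median HR falls from 1.50 (γ = 0) to 1.31 (γ = 1.0) and rejection from 35.4% to 18.2%. With it, HR stays near 1.5 and rejection at 33.8% to 35.7%.
- **N = 60, HR 2.0.** Rejection falls from 58.3% to 30.4% without the score and stays at 56.1% to 58.8% with it.
- **HR 1.0.** Both models centre on 1 with rejection near 5%.

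**Large samples.** Share of the log-HR kept = ln(HR without score) / ln(HR with score). At γ = 0.5: ln 1.790 / ln 1.991 = 0.85 for HR 2.0, and ln 1.415 / ln 1.490 = 0.87 for HR 1.5. At γ = 0.25 it is 0.95; at γ = 1.0 it is 0.65 to 0.69.

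**Chance imbalance.** The standard deviation of the between-arm difference in mean standardised score is √(1/60 + 1/30) = 0.22 SD, or √(1/40 + 1/20) = 0.27 SD at the smaller size. At γ = 0.5 a one-standard-deviation imbalance at N = 90 is worth roughly 0.5 × 0.22 = 0.11 on the log-HR scale. That is sampling variation, not bias, but adjustment would account for it.

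**The case against.** The strongest reply has five parts.

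1. **The SAP never says that the score is excluded.** A reader might infer a deliberate strata-only model. The text is silent on covariates and strata alike, so the documented defect is under-specification. This stands, although the plain reading of the sentence still yields a model without the score.
2. **The strata-only hazard ratio is not wrong.** A reader might infer that it is biased and understates any effect. Hazard ratios are non-collapsible: the age-stratified marginal hazard ratio is a valid estimand and matches the unadjusted Kaplan-Meier and logrank displays. It differs from the conditional one only when there is an effect and the score is prognostic. This stands, but the SAP does not say which is meant.
3. **There is no planned power to lose.** SAP 4.2 rules out formal hypothesis testing for efficacy, and the sample size rests on PK precision. The rejection rates above measure sensitivity, not a design property that has been missed. This stands.
4. **The adjusted effect estimate is already planned.** The AFT model is the named estimator and includes the score. This stands, and it limits the consequence to the supplementary hazard ratio.
5. **The protocol does not require the adjustment.** Protocol 11.6 has the words "Baseline subject characteristics will be included (in particular baseline score"), but they concern the linear mixed model for symptom scores over time and depend on the characteristics proving predictive. A reader might infer a protocol conflict; there is none. The sentence supports adjustment by analogy only.

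Adjusting the Cox model will also not force agreement with the AFT result. If a lognormal or log-logistic shape is chosen, the scales differ and proportional hazards would not hold. The fix removes one avoidable source of disagreement.

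**Conclusion.** The point holds as a gap in specification with a cheap and better alternative. Followed literally, the Cox sentence gives a marginal hazard ratio beside a conditional time ratio, without saying so.

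The cost depends on how prognostic the baseline score is, which the documents do not quantify. It is negligible at 0.25 log-HR per SD (HR 2.00 to 1.93, about 95% of the log-HR kept). It is material at 0.5 per SD (about 85% kept, and 12 points of rejection rate at N = 90 and HR 2.0: 77.6 - 65.5 = 12.1). It is larger beyond that. These figures rest on the assumed effect sizes and Weibull times. Under no treatment effect neither model is biased, and the AFT estimate is untouched.

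**What to change.** Replace the Cox sentence in SAP 4.2.3 with:

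*A Cox proportional hazards model stratified by age category, with treatment group and the respective baseline composite symptom score (7 or 10 symptoms) as covariates, will be used to derive the (conditional) hazard ratio.*

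Apply it to the resolution and definitive-resolution analyses.

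Cost: one sentence and one model term, with no new data. There are two small downsides. Subjects who still have no baseline score after the two-hour fallback in SAP 3.1.6 drop out of the Cox model, as they do from the AFT model; their number should be reported. And a conditional hazard ratio does not correspond directly to the unadjusted Kaplan-Meier and logrank displays, so a table footnote should say which hazard ratio is shown. If the sponsor prefers the marginal hazard ratio, the sentence should say so and name age category as the stratum.

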10.2. Discontinuation of Study Treatment

If a subject's study treatment must be discontinued before the end of the treatment regimen, this will not result in automatic withdrawal of the subject from the study.

A subject's study treatment should be discontinued if:

- The investigator believes that for safety reasons (eg, AE) it is in the best interest of the subject to discontinue study treatment
- The subject becomes pregnant
- The subject undergoes mechanical ventilation
- The subject requires peritoneal dialysis, hemodialysis, or hemofiltration
- The subject has an eGFR ≤ 30 mL/min/1.73 m² according to the MDRD equation
- The subject experiences any of the laboratory abnormalities as specified in Section [9.3.6](#), Specific Toxicities.

If a subject prematurely discontinues study treatment, follow-up assessments should be obtained and scheduled assessments should be continued. If a subject drops out due to withdrawal of consent, he or she will be offered an optional Safety Follow-up Visit.

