Resolution of influenza symptoms is defined as the first of a successive series of 2 recordings in which all symptom scores for each of the 2 assessments are 0 or 1 for all 7 primary influenza symptoms of the Flu-iiQTM (cough, sore throat, headache, nasal congestion, feeling feverish, body aches or pains, and fatigue (tiredness)). If the first record of a successive series of 2 recordings of resolved influenza is before day 14 in the evening then the 2 successive recordings should have been done over 3 scheduled successive analysis timepoints, 1 missing timepoint is allowed. If the first record of a successive series of 2 recordings of resolved influenza is at or after the evening record of Day 14 then the 2 successive recordings should have been done within 2 scheduled successive analysis timepoints (no missing allowed).

In cases where there are no sufficient recordings of resolved influenza as defined above, the endpoint will be censored. Censoring will be at the first

time of resolved influenza symptoms, if and only if after this observation there is no recording of non-resolved influenza symptoms (ignoring missing recordings). If there are no recordings of resolved symptoms satisfying this criterion, the time of censoring is the first possible time point a diary entry could have been made after the last observation of the presence of influenza, which is 20:00 on the same day if the last observation was a morning diary entry (from 3:01 until 15:00), 8:00 the next day if the last entry was an evening diary (from 15:01 until 03:00) (Day 1 until Day 14, morning). If the last observation of the presence of influenza is on Day 14 in the evening or after day 14 then the time of censoring is the time of the last diary entry + 24 hours. One exception is censoring at the Day 28 Visit (last study day for the subject). If the subject is not recovered on this day, the time of the last diary entry will be taken as the time of censoring.

Subjects who discontinue the study before resolving influenza symptoms and have an adverse events being reported as influenza complication ongoing on the day of discontinuation of the study will be censored at day 28, 20:00.

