Per module of the FLU-iiQ™ questionnaire on the impact of influenza a time to resumption of normal activities is defined as the time in hours from the first dose of investigational product till the first one of a successive series of 2 recordings where all scores in the FLU-iiQ Module are reported as “no difficulty” (Module 2: usual activities), “not at all” (Module 3: emotional impact) or “not at all concerned” (Module 4: impact on others). If the first record of a successive series of 2 recordings of resumption of normal activities is before day 14 in the evening then the 2 successive recording should have been done over 3 scheduled successive analysis timepoints, 1 missing timepoint is allowed. If the first record of a successive series of 2 recordings of resumption of normal activities is at or after the evening record of Day 14 then the 2 successive recording should have been done within 2 scheduled successive analysis time points.

Censoring will be done similar to the time to resolution of influenza, taking into account the possible time points a diary entry could have been made after the last observation of difficulties in usual activities, which is 20:00 on the same day if the last observation was a morning diary entry and 8:00 the next day if the last entry was an evening diary entry (Day 1 until Day 14, morning). If the last observation of difficulties in usual activities is on Day 14 in the evening or after Day 14 then the time of censoring is the time of the last diary entry + 24 hours. One exception: if no resumption of usual activities is

observed at Day 28, the time of the last diary entry will be taken as the time of censoring

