The time to return to usual activity and the time to return to usual health are defined as the time in hours from the first dose of investigational product till the first one of 2 successive cases where the response is 'Yes' on respectively FLU-PRO additional question 7 and FLU-PRO additional question 9. Missing data within the series are allowed as long as within three successive planned recordings there is at most 1 recording missing.

In cases where there are no sufficient recordings of return to usual activity/health as defined above, the endpoint will be censored. Censoring will be at the first time of return to usual activity/health, if and only if after this observation there is no recording of difficulties in usual activities/health (ignoring missing recordings). If there are no recordings of return to usual

activity/health satisfying this criterion, the time of censoring is the time of the last diary entry + 24 hours. One exception is censoring at the Day 28 Visit (last study day for the subject). If the subject is not returned to usual activity/health on this day, the time of the last diary entry will be taken as the time of censoring.

Data will be presented using Kaplan-Meier curves and Kaplan-Meier estimates by treatment group, overall and by age group. For a comparison between treatment arms, the time to parameters will be analyzed using an accelerated failure time model. The model will use the parametric shape, selected based on the goodness of fit criterion (AIC), and may take a Weibull, log-logistic, lognormal, or gamma distribution. As baseline covariates the ordinal scale at baseline category (ICU, ward+O₂, ward-O₂) and the age category (≥ 18 - < 65 years, ≥ 65 - ≤ 85 years) will be included. If the data don't provide an acceptable model fit, alternatively a Cox proportional hazards model can be used (in case the hazards are proportional). In case a Cox proportional hazards model is used a Log-log plot of survival will be added to check the proportional hazard assumption. Additionally, the time to event data will be analyzed using the logrank test and Gehan-Wilcoxon method.

- **Time to significant reduction in influenza symptom severity.**

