The time to significant reduction in influenza symptom severity (to mild or none for all influenza symptoms) is defined as time in hours from the first dose of investigational product until the first of 2 successive recordings in which the total score for each of the 2 recordings are lower or equal to 1 and all the domain scores are lower or equal to 1. The 2 successive recordings should have been done within 3 scheduled successive analysis timepoints (one missing in between is allowed).

Censoring will be done similar to the FLU-PRO time to return to usual activity and time to return to usual health as specified above.

Data will be presented using Kaplan-Meier curves and Kaplan-Meier estimates. For a comparison between treatment arms, the time to significant reduction in influenza symptom severity will be analyzed using an accelerated failure time model. The model will use the parametric shape, selected based on the goodness of fit criterion (AIC), and may take a Weibull, log-logistic, lognormal, or gamma distribution. As baseline covariate the age category (≥ 18 - < 65 years, ≥ 65 - ≤ 85 years) and baseline FLU-PRO total score will be included. If the data don't provide an acceptable model fit, alternatively a Cox proportional hazards model can be used (in case the hazards are proportional). In case a Cox proportional hazards model is used a Log-log plot of survival will be added to check the proportional hazard assumption. Additionally, the time to event data will be analyzed using the logrank test and Gehan-Wilcoxon method.

- **Proportion of patients with a significant reduction in influenza symptom severity.**

The proportion of subjects with a significant reduction in symptom severity (the total score for each of the 2 recordings are lower or equal to 1 and all the domain scores are lower or equal to 1) at each assessment will be tabulated.

4.2.7. *FLU-iiQTM Additional Daily Diary Items*

For the 9 additional daily diary items of FLU-PRO frequency distributions of the number (%) of subjects per additional FLU-PRO item and per response category will be shown at baseline and all post-baseline assessments, per treatment group.

4.2.8. *Correlation between viral load, viral titer and changes in clinical symptoms*

- **Correlation between the decline in viral load, the decline in viral titer and clinical symptoms**

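### The SAP's Day 28 censoring rule for unresolved drop-outs with a complication is absent from the FLU-PRO recovery endpoints, and on FLU-iiQ it misses subjects who stop the diary without leaving the study

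*SAP*

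**What the plan says.** **FLU-iiQ.** For time to resolution, SAP 4.2.3 gives a default and a special rule. By default, an unresolved subject is censored at the next possible diary slot up to the morning of Day 14, 24 hours after the last entry from the evening of Day 14, and at the last entry itself at the Day 28 visit. The special rule concerns "Subjects who discontinue the study before resolving influenza symptoms and have an adverse events being reported as influenza complication ongoing" on the day they leave; they are held to the end of follow-up ("discontinuation of the study will be censored at day 28, 20:00"). Definitive resolution inherits this ("Also censoring will be done similarly as for the Time to Resolution of Influenza"). So do the impact modules in SAP 4.2.4 ("Censoring will be done similar to the time to resolution of influenza"), although that section restates only the default times.

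**FLU-PRO.** SAP 4.2.6 writes out its own censoring for return to usual activity and usual health. If no qualifying recovery is recorded, "the time of censoring is the time of the last diary entry + 24 hours", or the last entry itself at the Day 28 visit. It contains no complication rule and no reference to 4.2.3. Significant symptom reduction follows suit: "Censoring will be done similar to the FLU-PRO time to return to usual activity and time to return to usual health as specified above".

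**Leaving the study.** Protocol 10.2 lists mechanical ventilation among the reasons to stop study treatment and says of stopping treatment that "this will not result in automatic withdrawal of the subject from the study". Protocol 10.3 limits withdrawal from the study to loss to follow-up, withdrawn consent and death.

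**The concern.** The special rule in 4.2.3 recognises that a subject who disappears while ill should not be treated as if he or she would have recovered like those still reporting. The SAP applies this to one questionnaire and not to the other, and gives no reason. It also ties the rule to formal departure from the study, which is not the same as ceasing to provide diary data.

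Censoring at the last entry takes these subjects out of the risk set as if their future were that of the remaining subjects. If they are in fact the non-recoverers, the Kaplan-Meier proportion recovered is too high. If the arms differ in how many subjects deteriorate and fall silent, part of that difference disappears from the reported time ratios and curves. Three named secondary endpoints are affected in full, and the FLU-iiQ endpoints in part.

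**Working it through.** **1. The same subject under each rule**

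| Subject, unrecovered at last diary entry | FLU-iiQ (4.2.3, 4.2.4) | FLU-PRO (4.2.6) |
|---|---|---|
| Leaves the study, complication AE ongoing | Day 28, 20:00 | last entry + 24 h |
| Dies, complication AE ongoing (death is a withdrawal reason in Protocol 10.3) | Day 28, 20:00, if death counts as discontinuing the study | last entry + 24 h |
| Stays in the study (e.g. ventilated, treatment stopped), diary never resumes | next slot, or + 24 h from Day 14 evening | last entry + 24 h |
| Keeps or resumes the diary | followed normally | followed normally |

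**2. FLU-iiQ delay up to Day 14 morning**

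The windows and slots are those of SAP 4.2.3.
- Morning entry, 03:01 to 15:00, censored at 20:00: from 20:00 − 15:00 = 5 h to 20:00 − 03:01 = 16 h 59 min.
- Evening entry, 15:01 to 03:00, censored at 08:00 next day: from 08:00 − 03:00 = 5 h to 08:00 − 15:01 the day before = 16 h 59 min.

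So the delay is 5 to about 17 h.

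**3. Size (illustration)**

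The documents give no deterioration rate, diary-loss rate or planned effect for these endpoints, so there is no figure to reproduce. Assumed: 60 active and 30 control subjects (the plan's 2:1 ratio at 90); recovery time lognormal with median 9 days and log-SD 0.7 in both arms; a severe share that makes its last entry on Days 1 to 5, never resumes and does not recover by Day 28. Analysis: a lognormal accelerated failure time (AFT) model with treatment only, 600 simulated trials.

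*Check on the recovery curve.* Among non-severe subjects, the proportion recovered by Day 28 is Φ(ln(28/9)/0.7) = Φ(1.135/0.7) = Φ(1.62) ≈ 0.95. With severe share p, the true proportion is (1 − p) × 0.95: 0.76 for p = 20%, and 0.85 to 0.86 for p = 10%. Last-entry censoring reports close to 0.95 whatever p is, so the overstatement is about 0.95 × p.

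| Severe, active / control | Time ratio, last entry + 24 h | Time ratio, Day 28 | Recovered by Day 28, active / control, last entry | Same, Day 28 rule |
|---|---|---|---|---|
| 5% / 5% | 1.00 | 1.00 | 0.95 / 0.94 | 0.90 / 0.90 |
| 10% / 10% | 1.00 | 1.00 | 0.95 / 0.95 | 0.85 / 0.85 |
| 5% / 15% | 0.98 | 0.85 | 0.95 / 0.95 | 0.90 / 0.80 |
| 10% / 20% | 0.98 | 0.85 | 0.95 / 0.95 | 0.86 / 0.76 |
| 15% / 5% | 1.02 | 1.16 | 0.95 / 0.95 | 0.81 / 0.90 |
| 20% / 10% | 1.02 | 1.18 | 0.94 / 0.94 | 0.76 / 0.85 |

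A ratio below 1 means faster recovery on active.

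**4. Dependence on permanent diary loss**

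A second illustration used a Cox model, median recovery 7 days, log-SD 0.6 and deterioration in 20% of control and 10% of active subjects. With total diary loss, the recovery hazard ratio is 1.30 under Day 28 censoring and 1.01 to 1.03 (separate simulation runs) under last-entry censoring. If only a quarter of the deteriorating subjects stop the diary for good and the rest are followed unrecovered to Day 28, it moves only from 1.28 to 1.23, and control recovery from 79% to 83% (150 trials).

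**The case against.** **The affected group may be small.** Both rules run from the last diary entry, so a sick subject who goes on answering is followed to Day 28, and one who resumes after ventilation is not censored at ventilation. Staff or caregivers may read the questions and record the replies (Protocol 9.4.1.1), and scheduled assessments continue after treatment stops. That a ventilated subject leaves no entries is an inference from the requirement that answers be the subject's own. This stands. A reader might infer that every ventilated subject, or the sickest in general, is censored within a day; the documents do not support that.

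**Deterioration is analysed elsewhere.** Death and ICU or ventilation are the worst levels of the Day 8 ordinal scale. Respiratory failure, ICU admission and mortality to Day 28 enter the complication analysis, and ICU stay is summarised. This stands, and the trial as a whole does not lose the information. It does not correct the symptom and function curves.

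**The instruments differ anyway.** FLU-iiQ resolution, the FLU-PRO domain thresholds and the yes/no return items can disagree under any censoring rule, so a disagreement is not in itself proof of the defect. That is right, but it gives no reason to handle the same drop-out differently.

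**The size is built in by assumption, and hypothesis testing is not planned.** Both are true. The figures show direction and dependence and are not a forecast. Estimation-only status lowers the stakes, but the time ratios, confidence intervals and curves will still be reported.

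**Conclusion.** The inconsistency is established from the text alone. The Day 28 rule covers FLU-iiQ only and requires departure from the study. All three FLU-PRO recovery endpoints lack it. On FLU-iiQ it also misses a subject who remains in the study but stops the diary for good while unrecovered.

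The resulting censoring is informative to the extent that these subjects fare worse than those still reporting. It then overstates recovery and pulls the treatment comparison towards no difference, hiding benefit or harm alike. A reader might infer that it works specifically against the drug; that would need deterioration rates by arm, which the documents do not give. With equal rates and the same diary loss in both arms, the illustration shows no bias in the treatment ratio, only an overstatement of recovery of about 5 to 10 points at shares of 5% to 10%.

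The point is worth correcting but does not threaten the trial's main purpose. The endpoints are secondary and descriptive; the primary pharmacokinetic objective and the sample size are unaffected.

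**What to change.** Carry the Day 28 rule of SAP 4.2.3 into 4.2.6, and state it explicitly in 4.2.4 instead of relying on a loose cross-reference. In all three sections, censor at Day 28, 20:00 any subject who is unrecovered at the last diary entry and who, when diaries stop for good, has died, is in ICU or ventilated, or has an influenza-complication adverse event ongoing, whether or not the subject formally left the study. Keep the present censoring times for all other missing diaries. Report the current last-entry censoring as a sensitivity analysis. A competing-risk analysis would be a defensible alternative if it is applied to both instruments.

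The cost is SAP wording and programming before unblinding; the plan already analyses deaths, ICU stay, ventilation status and complications. The downside is that a few subjects whose recovery went unrecorded will count as unrecovered, including some with only a minor complication ongoing. That can shift the estimate in either direction, so it should not be presented as conservative; the sensitivity analysis will show how much depends on it.
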